10.3 METHODS USED TO MINIMIZE BIAS AND MAXIMIZE VALIDITY

10.3.1 Multiple Sites

Subject enrollment will be conducted using at least three sites for each indication with up to nine sites in total for the study. This will reduce the effect of observer bias that might arise at a particular clinical site. As well as maximize the range of subjects treated.

10.3.2 Retrospective Consecutive Enrollment

To minimize any potential for selection bias consecutive enrollment will be utilized to retrospectively enroll any subjects encountered that meet the inclusion/exclusion criteria.

10.3.3 Balanced Covariates

The inclusion/exclusion criteria will be generalizable and applicable to the widest possible subset of the population requiring arthroscopic or open surgery for soft tissue repair. These criteria will be uniformly applied so as to enroll a cohort of subjects with similar symptoms and clinical requirements. This should maximize the applicability to as many subjects with similar baseline characteristics and help to bolster external validity.

10.3.4 Subject Attrition

Subject attrition for the sample size has been accounted for in the estimate of the Confidence Interval so as to validate the analysis and most efficiently use the available subjects.

10.3.5 Pre-specification of Statistical Analysis

The primary outcome measure has been pre-specified as well as the type of statistical analysis to be performed to evaluate clinical success so as to minimize reporting bias. The details of the analysis will further be pre-specified in the Statistical Analysis Plan (SAP) so as minimize any threats to external validity and yield clinically relevant estimates of effects and precision.

CONFIDENTIAL AND PROPRIETARY

This document contains information that is confidential and proprietary to Smith & Nephew PLC and Smith & Nephew, Inc. and is intended for use only by Smith & Nephew and its manufacturer. It shall not be reproduced or copied in whole or in part, nor shall the contents be disclosed by any means without prior written permission from Smith & Nephew, nor shall anyone make any use of it that is contrary to the expressed or implied wishes of Smith & Nephew.

Study Protocol—Device	
Safety and Performance of Q-Fix™ All-Suture Anchor System	Number: 17-5010-11
	Version: 2.0 05SEP2019
	Page: Page 25 of 62

11. STUDY PROCEDURES

11.1 VISITS AND EXAMINATIONS

11.1.1 Summary

For a summary of the required procedures by visit, refer to Table 11.1-1: Study Procedures by Visit.

Table 11.1-1: Study Procedures by Visit

Schedule of Events	Chart Review ^{1,2}		
	Screening	182 days post-op 6M (±91 Days)	365 days post-op 12M (± 91 Days)
Inclusion/Exclusion	X		
Case History Review***	X		
Implant Status ³	X	X	X
VAS	X	X	X
ROM	X	X	X
Concomitant Medications, Procedures ⁴	*	*	*
AE Assessment	*	*	*
Study Implant Disposition	*	*	*
Serious Adverse Event (SAE) / Adverse Device Effect (ADE) / Device Deficiency (DevD) Assessment	*	*	*
End of Study/Subject disposition	*	*	*

¹ Given the retrospective study design, data will be collected to the extent it is available.

² Informed consent/waiver of informed consent from the IRB must be obtained prior to retrospective data collection.

CONFIDENTIAL AND PROPRIETARY

This document contains information that is confidential and proprietary to Smith & Nephew PLC and Smith & Nephew, Inc. and is intended for use only by Smith & Nephew and its manufacturer. It shall not be reproduced or copied in whole or in part, nor shall the contents be disclosed by any means without prior written permission from Smith & Nephew, nor shall anyone make any use of it that is contrary to the expressed or implied wishes of Smith & Nephew.

Study Protocol—Device	
Safety and Performance of Q-Fix™ All-Suture Anchor System	Number: 17-5010-11
	Version: 2.0 05SEP2019
	Page: Page 26 of 62

³ Subjects who have undergone a revision procedure of the anchor will be considered terminated from the study from the date of the revision. Study related data will not be collected following the date of the revision.

⁴ Any concomitant medications/ procedures associated with an AE, SAE or SADE will be recorded.

* If applicable

*** Review of subject demographics, medical history, operative, post-operative, discharge, and cumulative AE's occurring since date of surgery

CONFIDENTIAL AND PROPRIETARY

This document contains information that is confidential and proprietary to Smith & Nephew PLC and Smith & Nephew, Inc. and is intended for use only by Smith & Nephew and its manufacturer. It shall not be reproduced or copied in whole or in part, nor shall the contents be disclosed by any means without prior written permission from Smith & Nephew, nor shall anyone make any use of it that is contrary to the expressed or implied wishes of Smith & Nephew.

Study Protocol—Device	
Safety and Performance of Q-Fix™ All-Suture Anchor System	Number: 17-5010-11
	Version: 2.0 05SEP2019
	Page: Page 27 of 62

11.1.2 Retrospective: Screening

Given the retrospective study design, data will be collected to the extent it is available.

- Obtain informed consent, as required by the IRB, on and IRB approved ICF or a waiver of informed consent as detailed in Section 9.5
- Do not proceed until consent has been obtained -----**
- Screen the subject for protocol inclusion/exclusion criteria.
 - Assign the subject a subject ID
 - Collect the following retrospective data, to the extent is available in the subject’s medical records, per CRF completion guidelines:
 - Case History Review (Review of subject demographics, medical history, operative, post-operative, discharge, and cumulative AE’s occurring since date of surgery)
 - Implant status
 - VAS (pain) – preoperative if available
 - ROM - preoperative if available
 - Implant Status CRF, if applicable
 - Study Implant Disposition CRF, if applicable
 - AE assessments- if applicable
 - Concomitant medications/ procedures associated with an AE, SAE or SADE will be recorded- if applicable
 - End of Study CRF, if applicable

11.1.3 Retrospective Data Collection: 6 Months Post-Operative (±91 Days)

Given the retrospective study design, data will be collected to the extent it is available

- VAS (pain) – post-operative if available

CONFIDENTIAL AND PROPRIETARY

This document contains information that is confidential and proprietary to Smith & Nephew PLC and Smith & Nephew, Inc. and is intended for use only by Smith & Nephew and its manufacturer. It shall not be reproduced or copied in whole or in part, nor shall the contents be disclosed by any means without prior written permission from Smith & Nephew, nor shall anyone make any use of it that is contrary to the expressed or implied wishes of Smith & Nephew.

Study Protocol—Device	
Safety and Performance of Q-Fix™ All-Suture Anchor System	Number: 17-5010-11
	Version: 2.0 05SEP2019
	Page: Page 28 of 62

- ROM - post-operative-operative if available
- Implant Status CRF, if applicable
- Study Implant Disposition CRF, if applicable
- AE assessments- if applicable
- Concomitant medications/ procedures associated with an AE, SAE or SADE will be recorded- if applicable
- End of Study CRF, if applicable

11.1.4 Retrospective: 12 Months Post-Operative (±91 days)

- VAS (pain) – post-operative if available
- ROM- post-operative-operative if available
- Implant Status
- Study Implant Disposition CRF, if applicable
- AE assessments- if applicable
- Concomitant medications/ procedures associated with an AE, SAE or SADE will be recorded- if applicable
- End of Study CRF, if applicable

11.2 STUDY METHODS AND MEASUREMENTS

All Subjects

- VAS pain assessment*
- ROM assessment*

**Patient Reported Outcomes (PROs) are optional and used according to the Investigator’s preference*

CONFIDENTIAL AND PROPRIETARY

This document contains information that is confidential and proprietary to Smith & Nephew PLC and Smith & Nephew, Inc. and is intended for use only by Smith & Nephew and its manufacturer. It shall not be reproduced or copied in whole or in part, nor shall the contents be disclosed by any means without prior written permission from Smith & Nephew, nor shall anyone make any use of it that is contrary to the expressed or implied wishes of Smith & Nephew.

Study Protocol—Device	
Safety and Performance of Q-Fix™ All-Suture Anchor System	Number: 17-5010-11
	Version: 2.0 05SEP2019
	Page: Page 29 of 62

12. STATISTICAL DESIGN

An SAP will be written and finalized prior to database lock. The SAP will account for any changes or deviations from the projected analyses in this protocol.

12.1 GENERAL

Smith & Nephew’s Global Biostatistics group or designee will conduct the statistical analysis for this study. Unless otherwise stated, all significance tests will be two-sided, performed at the 5% significance level. Resulting p-values will be quoted and 95% two-sided confidence intervals will be generated where appropriate.

Where data summaries are specified, categorical and ordinal variables will be summarized with frequencies and percentages. Continuous variables will be summarized with the following summary statistics: number of observations, mean, median, standard deviation, minimum and maximum values. All analyses will be performed in SAS 9.3 (or later).

12.2 ANALYSIS POPULATIONS

The following analysis populations will be used for this study:

- **Safety Population (SAF):** This includes all subjects who enroll in the study who had previously undergone arthroscopic or open soft tissue repair using the Q-Fix™ All-Suture Anchor System i.e. subjects who only provide retrospective data.
- **Per-Protocol Population (PP):** This includes all subjects in the Safety Population, who have no significant protocol deviations and who meet all the inclusion/exclusion criteria.

12.3 EFFICACY ANALYSIS

12.3.1 Analysis of Primary Endpoint(s)

CONFIDENTIAL AND PROPRIETARY

This document contains information that is confidential and proprietary to Smith & Nephew PLC and Smith & Nephew, Inc. and is intended for use only by Smith & Nephew and its manufacturer. It shall not be reproduced or copied in whole or in part, nor shall the contents be disclosed by any means without prior written permission from Smith & Nephew, nor shall anyone make any use of it that is contrary to the expressed or implied wishes of Smith & Nephew.

Study Protocol—Device	
Safety and Performance of Q-Fix™ All-Suture Anchor System	Number: 17-5010-11
	Version: 2.0 05SEP2019
	Page: Page 30 of 62

Clinical success rate, defined as subjects without re-intervention at 6 months post-operative, as assessed by the surgeon:

The frequency of the subjects without re-intervention at 6 months together with percentage with a 95% CI will be reported. Clinical success rate for the entire sample, as well as by the position (i.e. the hip, shoulder and knee will be reported). This analysis will be carried out using the per protocol population as the primary analysis population with the safety population used for sensitivity analysis.

12.3.2 Analysis of Secondary Endpoint(s)

Clinical success rate, defined as subjects without re-intervention at 12 months post-operative, as assessed by the surgeon. The same type of analysis carried out on the primary endpoint would be implemented here as well.

Device-related re-intervention. All the above variables will be categorical in nature hence frequencies together with percentages will be tabulated for the entire sample as well as by the indication will be reported.

Clinical success rate on adolescents and young adults, defined as subjects ages 13-21 without re-intervention at 6 and 12 months post-operative, as assessed by the surgeon. The same type of analysis carried out on the primary endpoint would be implemented here as well.

Available data will be summarized and summary statistics tabulated.

12.4 SAFETY ANALYSES

All safety analyses will be conducted using the safety population. The number of incidences and number of subjects reporting all adverse events will be summarized both overall and by seriousness, severity,

CONFIDENTIAL AND PROPRIETARY

This document contains information that is confidential and proprietary to Smith & Nephew PLC and Smith & Nephew, Inc. and is intended for use only by Smith & Nephew and its manufacturer. It shall not be reproduced or copied in whole or in part, nor shall the contents be disclosed by any means without prior written permission from Smith & Nephew, nor shall anyone make any use of it that is contrary to the expressed or implied wishes of Smith & Nephew.

Study Protocol—Device	
Safety and Performance of Q-Fix™ All-Suture Anchor System	Number: 17-5010-11
	Version: 2.0 05SEP2019
	Page: Page 31 of 62

relationship to study device and outcome. Incidences and number of subjects reporting device deficiencies will also be summarized. Further summaries of safety data may be described in the SAP.

13. SAMPLE SIZE JUSTIFICATION

Precision Analysis will be used to assess the overall proportion of success for the Q-Fix™ All-Suture Anchor System. Then assuming a 5% lost to follow-up rate after the first year, a minimum of 90 subjects will be enrolled (based on the inclusion/exclusion criteria) in order to complete 84 evaluable subjects. The 90 subjects will be enrolled to allow a minimum of 28 patients with each of the following indications to be recruited: Shoulder, Hip and Knee. Based on the results of the Byrd et al²⁵ study which showed an failure rate of 1.6% in the use of the Q-Fix™ All-Suture Anchor System, this number of subjects is sufficient to estimate the proportion of success rate to within 11% by use of the two-sided 95% confidence interval (based on an estimate of the rate of clinical success being 95%).

14. ADVERSE EVENTS AND DEVICE DEFICIENCIES

Adverse Events (AE) related to the study implant, or procedure including Adverse Device Effects (ADE), Serious Adverse Device Effects (SADE), Unanticipated Serious Adverse Device Effect (USADE), and Device Deficiencies (DevD) occurring from the time of the surgery until revision or study completion must be recorded on the appropriate CRF and reported. If the event is known to have been previously reported to Smith & Nephew, this must be noted on the CRF. After consent, in addition to all events related to the implant or the procedure, all serious adverse events (SAE), regardless of causality, must be recorded on the appropriate CRF and reported to the Sponsor and IRB if necessary. Events leading to a revision should be reported at all times regardless of causality.

Adverse Device Effects (ADE) occurring after study completion will be handled as product complaints reportable by the Sponsor and will not be entered into the study database.

CONFIDENTIAL AND PROPRIETARY

This document contains information that is confidential and proprietary to Smith & Nephew PLC and Smith & Nephew, Inc. and is intended for use only by Smith & Nephew and its manufacturer. It shall not be reproduced or copied in whole or in part, nor shall the contents be disclosed by any means without prior written permission from Smith & Nephew, nor shall anyone make any use of it that is contrary to the expressed or implied wishes of Smith & Nephew.

Study Protocol—Device	
Safety and Performance of Q-Fix™ All-Suture Anchor System	Number: 17-5010-11
	Version: 2.0 05SEP2019
	Page: Page 32 of 62

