9.5 INFORMED CONSENT

Study sites will obtain Institutional Review Board (IRB) approval for this study.

An IRB waiver of informed consent for study participation should be requested for those subjects who meet eligibility criteria and have retrospectively completed a 12 month postoperative visit, are deceased, or are lost to follow-up, per IRB policy. If allowed, a retrospective data set will be collected on these subjects. A copy of the waiver of informed consent will be placed in the subject file.

A waiver or alteration of the requirements for obtaining informed consent can occur under any of the following three provisions set forth by the Department of Health and Human Health Services:

- Research in general: an IRB may waive or alter the requirement of informed consent under 45 CFR 46.116(d), provided that the IRB finds and documents that all of the following four conditions are met:
 1. the research involves no more than minimal risk to the participants;
 2. the waiver or alteration will not adversely affect the rights and welfare of the participants;
 3. the research could not practicably be carried out without the waiver or alteration; and
 4. Whenever appropriate, the participants will be provided with additional pertinent information after participation.

If an IRB waiver is not granted, then the informed consent shall be obtained from all study subjects according to ISO 14155 guidelines and all applicable national regulations. Potential subjects must be informed as to the purpose of the study and the potential risks and benefits known or that can be reasonably predicted or expected as described in the written consent form. The subject, or their legally authorized representative, will then **read, sign, and personally date** the IRB approved informed consent document(s) (see below for difficulties with reading and writing). If the subject is an adolescent ages 13-17 years old, a signed adolescent informed consent form will be required of the subject as well as a

CONFIDENTIAL AND PROPRIETARY

This document contains information that is confidential and proprietary to Smith & Nephew PLC and Smith & Nephew, Inc. and is intended for use only by Smith & Nephew and its manufacturer. It shall not be reproduced or copied in whole or in part, nor shall the contents be disclosed by any means without prior written permission from Smith & Nephew, nor shall anyone make any use of it that is contrary to the expressed or implied wishes of Smith & Nephew.

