10.2.3 Safety Endpoints

- Device-related re-intervention
- All adverse events (AEs) occurring from the time of surgery until revision or study completion
- Device related AEs and serious adverse events (SAE's)

CONFIDENTIAL AND PROPRIETARY

This document contains information that is confidential and proprietary to Smith & Nephew PLC and Smith & Nephew, Inc. and is intended for use only by Smith & Nephew and its manufacturer. It shall not be reproduced or copied in whole or in part, nor shall the contents be disclosed by any means without prior written permission from Smith & Nephew, nor shall anyone make any use of it that is contrary to the expressed or implied wishes of Smith & Nephew.

Study Protocol—Device	
Safety and Performance of Q-Fix™ All-Suture Anchor System	Number: 17-5010-11
	Version: 2.0 05SEP2019
	Page: Page 24 of 62

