14.2 REPORTING PROCEDURES

AEs of any kind and DevDs will be recorded in the applicable CRF and source notes. The Investigator will evaluate all AEs for relationship to the device and procedure, if applicable, seriousness, and severity.

CONFIDENTIAL AND PROPRIETARY

This document contains information that is confidential and proprietary to Smith & Nephew PLC and Smith & Nephew, Inc. and is intended for use only by Smith & Nephew and its manufacturer. It shall not be reproduced or copied in whole or in part, nor shall the contents be disclosed by any means without prior written permission from Smith & Nephew, nor shall anyone make any use of it that is contrary to the expressed or implied wishes of Smith & Nephew.

Study Protocol—Device	
Safety and Performance of Q-Fix™ All-Suture Anchor System	Number: 17-5010-11
	Version: 2.0 05SEP2019
	Page: Page 35 of 62

ADEs, SAEs, and DevDs will be submitted/entered into the CRF and reported to the Sponsor within 24 hours of the Investigator being informed about the event (Figure 14.2-1). For ADEs and DevDs, details of the product/procedure related to the event will be included and where applicable, pictures taken of the device. The deficient product should be retained for return to the sponsor unless it is contaminated (e.g. used dressings must not be retained). Updates to submitted information will be recorded in the CRF within 24 hours of the information being available to the Investigator.

[figure not shown]
All SAEs and ADEs will be reviewed by a medically qualified person appointed by the Sponsor to determine which, if any, meet criteria for expedited reporting to the regulatory authorities. The Investigator will inform the IRB of AEs according to the IRB requirements.

Depending on the nature of the AE, the Sponsor may request copies of the subject’s medical records, imaging, operative notes, as well as results of any relevant laboratory tests performed or other documentation related to the AE. If the subject was hospitalized, a copy of the discharge summary may be requested by the Sponsor and should be forwarded as soon as it becomes available. In certain cases, the Sponsor also may request a letter from the Investigator that summarizes the events related to the case.

CONFIDENTIAL AND PROPRIETARY

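### The opening paragraph of Protocol Section 14 sets a narrower, consent-dependent rule for recording adverse events than the all-AE safety endpoint and Section 14.2 require

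*Protocol*

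**What the plan says.** The opening paragraph of Protocol Section 14 works in steps.

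- From surgery, it covers "Adverse Events (AE) related to the study implant, or procedure including Adverse Device Effects (ADE), Serious Adverse Device Effects (SADE" and the other device-effect categories, together with device deficiencies. Those "occurring from the time of the surgery until revision or study completion must be recorded on the appropriate CRF and reported".
- It then widens the scope: "After consent, in addition to all events related to the implant or the procedure, all serious adverse events (SAE), regardless of causality" must also be recorded and reported.
- It closes with an exception: "Events leading to a revision should be reported at all times regardless of causality".

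Other parts of the plan are broader.

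- Protocol 10.2.3 lists as a safety endpoint "All adverse events (AEs) occurring from the time of surgery until revision or study completion". SAP 5.3 has the same endpoint.
- Protocol 12.4 says that the "number of subjects reporting all adverse events will be summarized", with breakdowns that include seriousness and relationship to the device. The SAP 7.9.4 table shells have cells for events not related to the device, both serious and non-serious.
- Protocol 14.2 states that "AEs of any kind and DevDs will be recorded in the applicable CRF and source notes".
- The schedule of events and Section 11.1.2 have the screening chart review take in adverse events accumulated since the operation. Appendix 23.2 (item 8) obliges the investigator to record each adverse event.

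On consent, Section 9.5 says that "An IRB waiver of informed consent for study participation should be requested" for eligible subjects who have already completed a 12-month visit, have died or are lost to follow-up. The Amendment 1 text describes the waiver as already granted for adults.

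**The concern.** The endpoint and the tables need every adverse event after surgery. A site working from the opening paragraph of Section 14 could leave out unrelated non-serious events altogether. It could also leave out unrelated serious events that came before consent, or that occurred in a subject who was never asked for consent. A site working from Section 14.2 would record all of them. Both sites could claim compliance.

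Three things are at stake. Counts of unrelated AEs and SAEs would depend on which passage a site followed and on consent status. The site's own relatedness judgment would help decide whether an event reaches the database at all, and the adverse event board named in SAP 7.4.4 can classify only what was recorded. Finally, SAP 7.7 treats failure to collect adverse events as a protocol deviation, but the conflict leaves open what counts as a failure.

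**Working it through.** The plan states no figure on this point, so the check is mainly a comparison of text.

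**Step 1. What each passage requires**

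| Event | Section 14, opening paragraph | Endpoint (10.2.3, SAP 5.3) and analysis (12.4, SAP 7.9.4) | Section 14.2 and Appendix 23.2 |
|---|---|---|---|
| Related AE or SAE, from surgery | Required | Counted | Recorded |
| Device deficiency | Required | Summarised under 12.4 | Recorded |
| AE leading to revision, any causality | To be reported | Counted | Recorded |
| Unrelated SAE, after consent | Required | Counted | Recorded |
| Unrelated SAE, before consent | Not named | Counted | Recorded |
| Unrelated SAE, subject under a waiver | Not stated | Counted | Recorded |
| Unrelated non-serious AE | Not named | Counted | Recorded |

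The passages agree on the first four rows and part on the last three. The last three rows feed the SAP table cells for events not related to the device.

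**Step 2. How much follow-up lies before any consent**

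Inputs: subjects at 6 months or less after surgery are excluded (Protocol 9.3). The 6-month point is day 182 and the 12-month point is day 365 ± 91 (SAP 7.4), so the 12-month window closes on day 365 + 91 = 456. I assume that consent, where taken, comes once the subject is past the 6-month limit.

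- Nominal 6-month period: 182/182 = 100% precedes consent.
- Nominal 12-month period: at least 182/365 = 50% precedes consent.
- Follow-up to the end of the 12-month window: at least 182/456 = 40% precedes consent.
- Subjects whose 12-month visit is already complete: all follow-up to that visit precedes waiver or enrolment.

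**Step 3. Two readings of the consent condition**

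- If it refers to the date of the event, the rule on unrelated SAEs misses the periods in Step 2. For waived subjects with a completed 12-month visit it captures almost nothing within the analysis windows.
- If it refers to the date of recording, every charted SAE is covered once consent or a waiver allows chart review to begin. The two SAE conflicts in the table then largely close.

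The text does not settle which is meant. On both readings the opening paragraph still does not name unrelated non-serious events, so a conflict with the endpoint remains.

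**The case against.** The best defence is that the opening paragraph is a minimum. It never excludes anything, and it speaks of events to be recorded and reported. Section 14.2 separates recording, which covers everything, from 24-hour reporting, which covers device effects, serious events and deficiencies. Section 14.2, the chart review and Appendix 23.2 all point the same way, so the opening paragraph is the outlier. That reading is available, and it is probably what was intended. But no order of precedence is stated, and if all events from surgery were already to be recorded, the step that widens the scope after consent would add nothing to recording.

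A reader might also infer more than the documents support.

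- That Section 14 as a whole never requires unrelated non-serious events. Section 14.2 is part of Section 14 and does require them.
- That waived subjects have no start point. The schedule footnote and Section 9.6 treat a waiver as the alternative to consent for data collection and enrolment, so a start can be inferred. It is simply not stated for recording adverse events.
- That unrelated deaths would disappear. The End of Study form captures why a subject left the study (Protocol 9.8.1), and SAP 7.6 counts cumulative deaths.
- That a fully waived site would lose all its unrelated events. No AE rates are given to support a figure, and the site would have to disregard Section 14.2, the chart review and the appendix.

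**Conclusion.** The conflict is real and should be resolved, but it is limited to events judged unrelated to the implant or procedure. Three groups are exposed: unrelated non-serious events, unrelated serious events before consent, and unrelated serious events in waived subjects. For these, sites can comply with different passages and produce counts that are not comparable.

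The primary endpoint is not affected, because it rests on revision dates (SAP 7.4.1) and events leading to revision are captured regardless of causality. Device-related safety endpoints are not affected either: related events are required from surgery, and Section 14.1.2 counts a possible relationship as related.

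The number of events at risk cannot be estimated from the documents. The proportions of follow-up above (at least 50% of the nominal year, at least 40% to day 456) describe exposed time, not missing events. For unrelated serious events they apply only if the consent condition refers to the event date.

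**What to change.** Replace the consent-based split in the opening paragraph of Section 14 with one recording rule that matches Sections 10.2.3, 12.4 and 14.2 and SAP 5.3. It would cover every AE and SAE documented in the chart, from index surgery until revision or the end of the study, regardless of causality and of whether consent was obtained or waived. Keep the narrower list, labelled as such, for expedited reporting to the sponsor, and cross-refer to Section 14.2.

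Narrowing the endpoint and the SAP tables to fit a limited abstraction would also remove the contradiction. It would, however, give up the all-AE endpoint and leave the site's relatedness judgment as the gate to the database.

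The cost is a protocol clarification and modest extra abstraction, since the chart review already covers adverse events since surgery. Any site that applied the narrow rule would need to re-check subjects already enrolled. Amendment 1 reports 106 + 99 + 24 = 229 subjects across five sites, which is the upper limit for that re-check as of the amendment. The documents do not say which rule the sites used.
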